2. RESEARCH INFORMATION	
2.1 Is the research title from the Ministry of Health's list of priorities:	2.1 : The list is issued every year and found on MoH website.
2.2 The purpose of doing the research: Postgraduate Study	
If the answer is others, please, specify:	
Click or tap here to enter text.	•

3. RESEARCH TOPIC

"Traumatic Spinal Cord Injury Community Survey Comprehensive Study in North, West and Kurdistan Region of Iraq"

Click or tap here to enter text

3.2 The Research Question:

How many numbers of individuals who infected with traumatic SCI according to assess (levels, causes, and type of therapy), and what are the side effects of injury from a psychological and social point of view?

3.2: Write down the smart research question.

3.3 Research Background (with references in Vancouver style):

Traumatic spinal cord injury (TSCI) is a devastating and life-changing event that affects both the local site of injury and the entire body, an SCI has far-reaching consequences for a person's functioning and health. This will loss of sphincter control that will be led to reactive depression. furthermore, which can hinder the rehabilitation process and reduce the quality of life, as compared with that of the general population (1). The initiative of international spinal cord injury data sets was proposed by the international spinal cord society (ISCoS) in collaboration with the American Spinal Injury Association (ASIA)(3). This injury has an increased internationally which it spreads as a result of violence, falling, sport, or car accidents. Most of countries in world had statistical data per year, but in Iraq this injury is less than another injury which is cared about it, so clearly there is no statistical numeric for this injury. Therefore, the study suggests that health promotion for those with disabilities, including those with SCI, has historically been directed at primary prevention of injury disability rather than prevention of secondary conditions (4). To answer on research question, the research will be developing International Spinal Cord Injury Data Sets is to gather consistent data elements to enable worldwide SCI data and outcomes to describe the health care, design, and initial findings of an Iraqi survey portraying the life situation of people with SCI living in the community. Specifically, the survey aimed to (a) identify the number of infected, reasons the proportion of people with SCI requiring services of community living, the levels of their injury, the type of therapy, and the extent of met and unmet needs, (b) determine the barriers or facilitators to service utilization, and (c) describe the outcome in the lives of people with SCI (occurrence of SHCs, degree of participation in major life areas including productive activities, quality of life) and their interrelationships with service needs (met and unmet).

3.3: Write concisely the scientific bases of your research question. Use updated and new references.

3.4 Justification of Choosing this topic (Rationale):

The researcher decided to choose this topic because the lack of research statistics on SCI during the war against ISIS, in addition the number of injured, the type, causes, and the levels of this injurie, as well as follow-up of the injured from a therapeutic, psychological and social point of view to detect the side effects of this injury and the level of rehabilitation for those individuals.

3.4: Show the rationale of choosing this research question and what are the expected gab that this research is going to fill.

3.5 The Objective/s of the Research:

The aim of this study is developing International Spinal Cord Injury Data Sets is to gather consistent data elements to enable describe the health care, design, and initial findings of an Iraqi survey portraying the life situation of people with SCI living in

3.4: Write down primary and secondary objectives

aimed to (a) identify the number of infected, reasons the proportion of people with SCI requiring services of community living, the levels of their injury, the type of therapy, and the extent of met and unmet needs, (b) determine the barriers or facilitators to service utilization, and (c) describe the outcome in the lives of people with SCI (occurrence of SHCs, degree of participation in major life areas including productive activities, quality of life) and their interrelationships with service needs (met and unmet).

4. Research Setting

4,1 When will the sample be collected?

Start 1

1 December 2019

End

31 January 2022

4.3 The resources needed from the institution selected to implement the research?

The resource needed tick		Amount and types		
Laboratory sample (Blood, urine,)		Click or tap here to enter text.		
Devices, instrument, tools		Click or tap here to enter text.		
Patients' or firm's records		Private and Government clinic and hospital and centers of physiotherapy and rehabilitation		
Persons (patients, employers)		Approximately about 100-150 patients and about 10-25 employers		
Others specified	\boxtimes	The experiment will be carried out with physical and functional tests, mostly in the patient's home	79	

4.4 Who will fund the research? Governmental

If the answer is others, please, specify:

And personal support

5. RESEARCH METHODOLOGY

5.1 Study Design: choose one from below

Case Control

If the answer is others, please, specify: Click or tap here to enter text.

5.2

Case Definition: individuals who have Traumatic Spinal Cord Injury (TSCI) at any level this cases study, and the others who healthy people without SCI as control study.

5.3 Exclusion Criteria:

Any case who has non traumatic SCI like pathology reasons and who don't commit in a protocol treatment or rehabilitation program, this will limit by Neuro physician according to history date for patients and some fustigations and according to ASIA scale for limit the level of injury and type complete or incomplete.

5.4 Sampling Methods:

The researcher will survey the centers of physiotherapy in general Hospital, private clinic, and Neuro disease to select the case which type of injury traumatic SCI and the expectation of number of sample study about (40-50) injuries. The researcher will be depended on form which will prepare, this form contains a personal information and some morphological measurements for example (Mass, Length, BMI...) and injury information as example (date of injury, date of rehabilitation, the stage of rehabilitation, type of medical intervention, level of injury, type of injury....) the research will in depend on medical fustigation for each patient and it will use the (ASIA) International Standards for Neurological Classification of Spinal Cord Injury (ISNCSCI) to access for date. And also another information which will be get it from researcher that is relate with the psychological and community integration by using a specific questionnaires for example (CES-D) Center for

5.1: write the design of the study that is going to answer your research question

- **5.2**: It is the operational definition used to enroll participants in the study
- **5.3**: the participants that fulfil case definition, but excluded from the study due to a specific cause
- **5.4**: the method used to select the participants of the sample from the targeted sample.

5.5: Write details about how to allocate participants in study arms or blinding them if the study design is relevant

Epidemiologic Studies Depression Scale(3), (CIQ) Community Integration Questionnaire, (SWLS) Satisfaction with Life Scale, (DASS-21) Depression, Anxiety and Stress Scale, and (SAS) Scale of after Strock. This study will accredit the questions within the questionnaire (Appendix) were developed on the basis of the 20 data elements in the ISCICDS. Of these, four neurological data elements are to be collected at acute admission and at final inpatient discharge, respectively: that is, date of neurological examination, sensory level (SL), motor level (ML) and ASIA Impairment Scale (AIS). Other data elements include date of birth, injury, acute admission and inpatient discharge, total days hospitalized, gender, injury etiology, vertebral injury, associated injury, spinal surgery, ventilatory assistance and place of discharge.

What is mentioned above will be made with case study, and about the control sample who will be as a same number of case study and they will answer on psychological and social questionnaire and this outcome will be depended as a standard for statistical comparing.

5.5 Randomization and Blinding Methods (If relevant):

This study will accredit the questions within the questionnaire (Appendix) were developed on the basis of the 20 data elements in the ISCICDS. Of these, four neurological data elements are to be collected at acute admission and at final inpatient discharge, respectively: that is, date of neurological examination, sensory level (SL), motor level (ML) and ASIA Impairment Scale (AIS). Other data elements include date of birth, injury, acute admission and inpatient discharge, total days hospitalized, gender, injury etiology, vertebral injury, associated injury, spinal surgery, ventilatory assistance and place of discharge.

Within the Spinal Cord Injury Core Data Documentation Questionnaire, the numbers of the first 12 questions correspond to the first 12 data elements within the ISCICDS. The remaining four questions are related to neurological data. To facilitate answering the questionnaire

Lastly, the results will disseminate on all governmental hospitals and rehabilitation centers.

5.6 Selection of Participants in control group (If Relevant):

The sample which will be as a control group will be from healthy people who don't have SCI to be a normal stander for comparison.

5.7 Definition of Outcomes and how to measure it:

The data will collect by depending on an official health documents for government physiotherapy and rehabilitation which care by TSCI information. Author will visit all specialism hospit.

TSCI and collect the number of injured, age, gender, level of injury according to ASIA Impairment Scale(8), causes of injury, type of intensive care, and type of treatment. The author will depend on a questionnaire adapted from the data elements within the ISCICDS which consist of multiple items and questions for data collecting and achieving the goals of study. According to the data collection form, the data within the ISCICDS can be collected in clinical settings. If the method of data collection used in clinical practice is in accordance with the information in the ISCICDS, then such data may be retrieved retrospectively from the charts, whereas other data will have to be collected using the guidelines contained in the ISCICDS to ensure consistency across centers. In this study, the practice of collecting information described in the ISCICDS in individuals with SCI performed by physicians in Iraq was investigated. A questionnaire adapted from the data elements within the ISCICDS was used to allow comparison between current practice and that described in the ISCICDS. The results of this study will provide a preliminary overview of SCI core data collection among Iraqi SCI physicians and hospitals. On the basis of these results, recommendations regarding data collection across Iraqi SCI centers will be elaborated to ensure that uniform data, comparable to other SCI centers worldwide, will be gathered.

5.6: Criteria of enrolling participants in the control group

5.7: Variables used to answer the research question. Write them in details; how do you measure them, when and by whom.

This study will accredit the questions within the questionnaire (Appendix) were developed on the basis of the 20 data elements in the ISCICDS. Of these, four neurological data elements are to be collected at acute admission and at final inpatient discharge, respectively: that is, date of neurological examination, sensory level (SL), motor level (ML) and ASIA Impairment Scale (AIS). Other data elements include date of birth, injury, acute admission and inpatient discharge, total days hospitalized, gender, injury etiology, vertebral injury, associated injury, spinal surgery, ventilatory assistance and place of discharge.

5.8 The Procedure (steps) of the Study:

The researcher will do survey study by touring on all Hospitals and centers which care with Neuro-disease and amount the number of cases and type, cause, level of injury as also the type of treatment. The researcher will interview will patients and collect some information by questionnaire to determine and assess the psychological and social case. All of three researches will have a control group sample for stander of all tests.

5.8: Steps of performing the study.

5.9 Statistical Analysis and sample size:

The researchers will do statistical analyze by using SPSS bag to out put the results. They will use T-test for similar sample pre-post test. And also, will use correlation person, spearman, LSD, Stander division, average, and some statistical tools which will determine next.

5.9: define types of variables. What are the statistical tools used to measure p value? How are you going to show your results? ... etc

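### Does the exclusion of spinal cord injury cases who do not commit to a rehabilitation programme bias the home-based rehabilitation comparison?

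*Combined protocol and SAP*

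**What the plan says.** The clause is in section 5.3 (Exclusion Criteria) of the combined protocol and SAP. After ruling out non-traumatic injury, it also excludes cases "who don't commit in a protocol treatment or rehabilitation program, this will limit by Neuro physician according to history date for patients". The sentence then adds "some fustigations and according to ASIA scale for limit the level of injury and type complete or incomplete". The form's side note to 5.3 explains what the field is for: "the participants that fulfil case definition, but excluded from the study due to a specific cause".

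The research topic in section 3 of that form is "Traumatic Spinal Cord Injury Community Survey Comprehensive Study in North, West and Kurdistan Region of Iraq". Section 5.1 selects a case-control design, 5.4 expects about 40 to 50 injured people, and 5.6 says the "control group will be from healthy people who don't have SCI". The form never names the HBRP. Three remarks suggest a wider project:
- Section 4.3 says "The experiment will be carried out with physical and functional tests, mostly in the patient's home".
- Section 5.8 says "All of three researches will have a control group sample for stander of all tests".
- Section 5.9 plans a "T-test for similar sample pre-post test".

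The HBRP study is described in the Protocol. Its Methods section reports 13 volunteers with SCI who chose their own group, 8 experimental and 5 first control, plus 5 healthy second controls. The experimental group followed a six-month programme. The Protocol's statistical paragraph names a two-way repeated-measures ANOVA at 0.05. The available Protocol text has no exclusion, withdrawal or analysis-set rule and does not refer to section 5.3.

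**The concern.** Whether someone commits to a programme may show only once it has begun, and the experimental group is the only one described as receiving one. If 5.3 governs the HBRP study and was applied during follow-up, it could remove poor adherers mainly from that group. If poor adherers would also have gained less, the group mean rises for a reason unrelated to the programme, and the comparison with the first control group favours the HBRP.

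A second worry is that, read as commitment to past rehabilitation, the clause seems to exclude the very people the Protocol studies, since its participants had stopped rehabilitation for 4 to 5 years.

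The Protocol gives no numbers excluded or analysed by group, so a reader cannot confirm directly which reading was used. At stake would be the credibility of the Summary's conclusion that the programme worked.

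**Working it through.** **1. Which study does 5.3 belong to?**

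| | Combined protocol and SAP | Protocol |
|---|---|---|
| Topic | Community survey of traumatic SCI | Six-month HBRP |
| Design | Case-control (5.1) | Voluntary controlled trial |
| People with SCI | About 40-50 (5.4) | 8 + 5 = 13 |
| Controls | Healthy only, as many as the cases (5.4, 5.6) | 5 with SCI and 5 healthy; total 13 + 5 = 18 |
| Exclusion rule | 5.3 | None in the available text |

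The form has no SCI control arm. The remarks in 4.3, 5.8 and 5.9 make a link to a home experiment possible, but none of them attaches 5.3 to the experimental versus first control comparison.

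**2. When does it act?** The heading, the side note, and the reliance on a physician, patient history and the ASIA scale all fit screening. This is a lean rather than proof, because history and ASIA may attach mainly to the traumatic/non-traumatic part. A willingness check made before people join, in both SCI groups, adds no bias to the comparison.

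**3. Does it contradict the study population?** The Protocol's Background attributes the interruption to inadequate programmes and to a mismatch with participants' circumstances. Stopping for those reasons is not plainly a failure to commit, so no contradiction is shown.

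**4. How large is the harm under the unfavourable reading?** The documents give no figure to reproduce. The number removed and the correlation r between commitment and outcome are assumptions. There is no true effect, SD means the SD of the 0-6 month change, and the least committed are removed from the experimental group only.

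*Shift = r × (minus the sum of the expected values of the removed lowest standard-normal order statistics) / (number kept).*
- 1 of 8 removed: 1.424/7 = 0.203. At r = 0.5 the shift is 0.10 SD.
- 2 of 8 removed: (1.424 + 0.852)/6 = 0.379. At r = 0.5 the shift is 0.19 SD.
- If the 8 reported are those left from 9 or 10: 1.485/8 = 0.186 and (1.539 + 1.001)/8 = 0.318. At r = 0.5 the shift is 0.09 or 0.16 SD.

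*95% CI half-width = t(0.975, n1 + 5 − 2) × √(1/n1 + 1/5).*
- n1 = 7: 2.228 × 0.5855 = 1.305 SD, and 0.102/1.305 = 8%.
- n1 = 6: 2.262 × 0.6055 = 1.370 SD, and 0.190/1.370 = 14%.

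*Error rate of the group-by-time F test.* This was simulated with 200,000 runs per cell, three time points, compound symmetry and a nominal 0.05. The Protocol does not say which groups enter the ANOVA, so both versions are shown. Cells give total error / significant and favouring HBRP.

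| Removed | r | Three groups | Two SCI groups |
|---|---|---|---|
| None | – | 5.1% / 2.6% | 5.0% / 2.5% |
| 1 of 8 | 0.5 | 5.4% / 3.3% | 5.5% / 3.5% |
| 2 of 8 | 0.5 | 5.8% / 4.0% | 5.9% / 4.3% |
| 1 of 8 | 1 | 6.7% / 4.8% | 6.8% / 5.1% |
| 2 of 8 | 1 | 8.8% / 7.3% | 9.2% / 8.1% |

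At r = 0 there is no shift. The rows at r = 1 are an upper bound for these numbers removed.

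A harsher case was simulated with a two-sample t-test (100,000 runs): 12 people start, the 8 most committed are kept, and r = 0.7. The shift is 0.36 SD and the error rate 11.0%. This requires four unreported removals, whereas the Protocol gives 8 as the number who joined.

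**The case for a change.** The best case for acting is that 5.3 is the only exclusion rule in the available text of either document. A pre-post test and commitment to a programme fit an intervention better than a one-time survey. The Protocol's Methods section says plans were personalised to keep people in for six months, so retention was a live issue, yet no rule covers someone who stops. Clarification would take a sentence and a participant count.

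Part of this stands. The scope and timing of 5.3 are unstated, and the numbers excluded and analysed by group are not reported. But the harm needs four things together: that 5.3 governs the HBRP study, that it acted after people joined and mainly in the experimental group, that someone was removed, and that commitment predicts outcome. The documents establish none of them. The Methods section gives 8 and 5 as the numbers joining, and the care of the first control group is not described, so removal from that group cannot be ruled out either.

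Nor would rewording the clause achieve much. The Protocol describes the HBRP as completed, so a new criterion cannot alter who took part. If anyone had been removed, their 3- and 6-month measurements might not exist, and an instruction to analyse all starters would not by itself recover them.

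**Conclusion.** No change to the plan follows. Section 5.3 is loosely worded, but it is an exclusion field in a survey form, it reads most naturally as screening, and nothing shows that it shaped the HBRP comparison. The silence on the analysis set is a gap that an analyst would ordinarily fill by keeping everyone who joined in their own group, with whatever measurements were recorded.

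Under the unfavourable reading, with 1 or 2 of 8 removed and a correlation of 0.5, the shift is 0.10 or 0.19 SD against a half-width of 1.30 or 1.37 SD. Total error rises from 5% to at most 5.9%. Even at a correlation of 1 it reaches 8.8% or 9.2% with two removed. Larger figures need more removals than the documents give any reason to assume. All these sizes rest on assumed removals and correlations.

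The documented weakness of this comparison is that participants chose their own group. That is a separate matter, and clarifying 5.3 would leave it untouched.

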#### Methods

This voluntary controlled trial included 18 volunteers split into three groups: 13 people with Spinal Cord Injury (SCI) their injuries time since (53.4-55) months. They joined voluntarily into Two groups, eight in the experimental group (Exp.) and Five in the first control (1st Con.); while five were healthy individuals in the second control (2nd Con.); all around (21.2) years old on average. As a first procedure, detailed interviews were conducted with each participant at the beginning of the study to gather information about their physical, psychological, and social well-being. This information helped the authors create personalized rehabilitation plans for each participant to ensure their

participation in the study for the entire 6 months period. Through our study objectives, the authors used body composition such as height, weight, BMI and some anthropometric measurements for body parts circumferences by using tape measurements, similar to a previous study by Akita et al. Also, muscle strength tests were performed on participants' lower and upper extremities, head, and trunk to measure various movements. The 2nd control group completed their measurements and tests at college. Additionally, a clinical test using the American Spinal Injury Association scale (ASIA) was conducted on each participant to assess sensory feeling and voluntary movement potential on both sides of the body.

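### Section 5.6 of the survey plan accepts any healthy person without spinal cord injury as a control and ties only their number to the cases, so case-control differences can mix the injury with sex and age

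*Combined protocol and SAP*

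**What the plan says.** The two documents describe different studies.

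The Combined protocol and SAP is the application for a community survey with a case-control design, expecting 40 to 50 cases (section 5.4). On the controls it says:

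- Section 5.2, within the case definition: "the others who healthy people without SCI as control study".
- Section 5.6, where the form asks for the control criteria: the "control group will be from healthy people who" are free of SCI, and they are to serve as the normal standard.
- End of the section 5.4 text, on how many: "control sample who will be as a same number of case study".
- Same place, on their use: "they will answer on psychological and social questionnaire and this outcome will be depended as a standard for statistical comparing".
- Section 5.8: "All of three researches will have a control group sample for stander of all tests". The three studies are not identified.

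Section 5.9 lists a pre-post t-test, Pearson and Spearman correlations, LSD and descriptive statistics, and leaves other tools to be chosen later. It names no covariate adjustment, stratification or matched analysis.

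The Protocol describes the home-based rehabilitation study: 8 experimental and 5 first-control participants with SCI, and 5 healthy people as second control. Its Methods give one average age of about 21.2 years for everyone and no sex or height by group, and add: "The 2nd control group completed their measurements and tests at college". Its analysis is a two-way repeated-measures ANOVA with no covariates named.

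**The concern.** In a comparison of injured with healthy people, the way the healthy people are chosen decides what the difference means. Here the controls define normal, but the rule for choosing them does not require them to resemble the cases in anything except number. Depression, anxiety, life satisfaction and community integration scores can differ by sex and age with no SCI effect at all. If the control group has a different sex ratio or age range from the cases, the difference reported as the psychological and social consequence of SCI will contain a part that is due to sex and age, in an unknown direction. Equal group sizes help precision but do nothing about this.

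**Working it through.** **Step 1: text check.** The documents state no power, effect size or SD, so there is no figure of the plan's own to reproduce.

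| Question | Survey plan |
|---|---|
| Who may be a control? | Healthy, no SCI (5.2, 5.6) |
| What is tied to the cases? | Number only (5.4) |
| Matching on sex or age? | None stated |
| Source population for controls? | None stated in 5.6 |
| Adjustment in the analysis? | None named (5.9); other tools left open |
| Age and sex recorded? | For cases (5.4, 5.7); not stated for controls, who answer the psychological and social questionnaires |
| Role of the controls | Standard for questionnaire scores (5.4) and for all tests (5.8) |

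So nothing in the selection rule prevents an imbalance, nothing in the analysis removes one, and it is not certain that one could be seen in the data.

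**Step 2: possible size of the bias.** The inputs are assumptions. For a binary factor such as sex, or being above a given age:

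bias = (effect of the factor on the score) × (difference in its prevalence between groups)

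- Low end: 0.3 SD × 0.30 = 0.09 SD.
- High end: 0.8 SD × 0.60 = 0.48 SD.

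The number of participants does not enter the formula, so recruiting more people does not reduce the bias.

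**Step 3: effect on a significance test.** Assume that SCI has no effect, 45 cases and 45 controls (the middle of 40 to 50), an unadjusted two-sided test at 5%, and a normal approximation. Let the factor have prevalence 50% in controls and 50% + d in cases, and effect e in within-stratum SDs. With controls fixed at 50%, d cannot exceed 50 points, so a separate grid of 10 to 40 points is used here.

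- Spurious difference: b = d × e.
- Variances: cases 1 + e²(0.5 + d)(0.5 − d); controls 1 + 0.25e².
- Example, d = 0.30 and e = 1: b = 0.30; variances 1.16 and 1.25; SE = √(2.41/45) = 0.231; b/SE = 1.30; chance of a significant result about 25%.

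| Prevalence difference | e = 0.5 SD | e = 1.0 SD | e = 1.5 SD |
|---|---|---|---|
| 10 points | 5.6% | 7.1% | 8.8% |
| 20 points | 7.5% | 13.7% | 21.1% |
| 30 points | 10.7% | 25.4% | 42.3% |
| 40 points | 15.3% | 41.9% | 67.7% |

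The nominal rate is 5%. The corresponding ranges are 5.5% to 62.6% with 40 per group and 5.7% to 72.3% with 50 per group. Small imbalances in weak factors do little harm; a 30-point imbalance in a factor worth 1 SD raises the error rate about fivefold.

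**Step 4: the home-based study.** With 8 experimental against 5 healthy participants, the same grid gives 5.1% to 14.3%. The error rate is lower only because the groups are so small; the bias in the estimate is the same. Each healthy person is also 1/5 = 20% of the reference mean.

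**The case against.** The best case for the plan is this. No imbalance is shown, and every input to the sizes above is assumed. The survey's objectives are largely descriptive. Section 5.9 leaves room for further methods. Section 4.2 is not in the text available for review, so a rule on setting there cannot be excluded. The home-based study asks whether the programme affects people with SCI; that can be addressed by the experimental versus first-control comparison and by change over time, neither of which depends on the healthy group.

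Most of this stands as a limit on the point. It does not remove it: section 5.6 is where control criteria belong, it is visible, and the plan explicitly makes the controls' scores the standard for statistical comparison.

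A reader might infer more than the documents support:

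- *That the equal-number rule is contradicted by 13 SCI and 5 healthy participants.* The rule belongs to the survey of 40 to 50 cases; the 13 and 5 belong to the home-based study. A difference between two studies is not an error in either.
- *That college students are the standard for the depression scores.* College appears only as the place where the home-based study's healthy group was measured. It is not given as a recruitment source, and that study lists no depression scale.
- *That war-area residence is a demonstrated confounder.* It is an inference from the setting; controls from the same regions would share the exposure.
- *That controls should be matched on body size.* Weight and BMI are outcomes in the Protocol, which also says limited movement may change them. Matching on them could remove part of the SCI effect.
- *That age clearly differs in the home-based study.* The average of about 21.2 years for all participants suggests otherwise, although it is a description and not a selection rule.

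**Conclusion.** The point holds for the survey plan. Its control rule allows sex and age to differ freely between cases and controls, and no named analysis corrects for this. The bias could be 0.09 to 0.48 SD if a factor is worth 0.3 to 0.8 SD and its prevalence differs by 30 to 60 points; it could also be near zero if the groups happen to be alike. The documents do not say which. The plan should be changed because the remedy is cheap and the comparison with controls is otherwise hard to interpret. The point does not show that any result is wrong, and it does not touch the comparison of the two SCI groups in the home-based study, whose voluntary allocation is a separate matter.

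**What to change.** - **Section 5.6:** recruit controls from the same areas as the cases, and frequency-match them to the cases on sex and age band. Do not match on weight or BMI.
- **Control form:** record age and sex, which the documents show only for cases.
- **Section 5.9:** name a case-control comparison of each score adjusted for age and sex, for example a linear model with group, age and sex. If controls are already enrolled, obtain their age and sex and make this adjustment; it is dependable only where the two groups overlap in age and sex.
- **Home-based study:** its Protocol is written in the past tense, so only the reporting can change. Present the 5 healthy people as a descriptive reference, with their sex, age and height, and rest conclusions about the programme on the experimental versus first-control comparison.

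The cost is somewhat slower recruitment of controls and two extra form fields. No additional patients are needed.
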